Study Title: Early Molecular Changes in Vitiligo After
Narrowband Ultraviolet Therapy

NCT No.: NCT03270241

04/12/2018

JHM IRB - eForm A – Protocol

- Use the section headings to write the JHM IRB eForm A, inserting the appropriate material in each. If a section is not applicable, leave heading in and insert N/A.
- When submitting JHM IRB eForm A (new or revised), enter the date submitted to the field at the top of JHM IRB eForm A.

1. Abstract

- a. Provide no more than a one page research abstract briefly stating the problem, the research hypothesis, and the importance of the research.

Vitiligo is a chronic acquired inflammatory skin disease reportedly affecting approximately 1% of the world's population. Patients with vitiligo often experience emotional disabilities that can severely impact their quality of life. There have been several studies that demonstrate the negative impact that vitiligo has on quality of life, which are comparable to other chronic skin diseases like atopic dermatitis, psoriasis, and acne. While the exact etiology of vitiligo is unknown, both the humoral and cellular immunity are believed to contribute to the pathogenesis of the disease. Histological and molecular differences are also observed between normal and vitiligo skin. Currently, narrow-band UVB (NB-UVB) irradiation, is the most common medical therapy available for vitiligo. NB-UVB has been observed to stimulate melanocyte migration and proliferation and exhibit immune-modulating effects.

Previous research studies observed that long-term NB-UVB phototherapy on vitiligo skin have demonstrated effectiveness and safety, both visually and molecularly. The current study aim to evaluate the molecular and histological impact of short-term NB-UVB treatment. We will perform patient and clinical evaluations along with skin biopsies from normal and vitiligo skin. We hypothesize after one week of NB-UVB treatment, there will be observable molecular changes in vitiligo-treated skin when compared to vitiligo untreated and normal skin.

2. Objectives (include all primary and secondary objectives)

Primary Objective: To evaluate the molecular changes from NB-UVB in Vitiligo treatment
Secondary Objective: To identify potential targets for further study and for treating Vitiligo.

3. Background (briefly describe pre-clinical and clinical data, current experience with procedures, drug or device, and any other relevant information to justify the research)

Vitiligo is a chronic acquired inflammatory skin disease reportedly affecting approximately 1% of the world's population (Kyriakis KP et al, 2009; Taieb A, 2007). Vitiligo remains primarily a clinical diagnosis and can be made with the help of the Wood's lamp, which is a handheld Ultraviolet (UV) irradiation device that emits UVA waves at 365 nm. The Wood's lamp can be particularly

helpful in determining the extent of vitiligo and assess the response to therapy (Gawkrodger DJ et al, 2008). Additionally, histopathology can confirm the diagnosis, usually showing few or absence of melanocytes and a sparse inflammatory cell infiltrate (Kim YC et al, 2008).

Patients with vitiligo often experience emotional disabilities that can severely impact their quality of life. There have been several studies that demonstrate the negative impact that vitiligo has on quality of life, which are comparable to other chronic skin diseases like atopic dermatitis, psoriasis, and acne. (Kent G et al, 1996; Radtke MA et al, 2009; Talsania N et al, 2010; Ongenaes K et al, 2009; Linthorst Homan MW et al, 2009; Parsad D et al, 2003) The most commonly applied metric is the Dermatology Life Quality Index (DLQI), a widely accepted and validated dermatology-specific patient quality of life assessment. This questionnaire consists of 10 questions evaluating social and functional impairments related to skin disease, based on a score ranging from 0 (no impairment) to 30 (severe impairment). (Finlay AY et al, 1994) Vitiligo has also been associated with psychiatric morbidity which can translate to significant psychosocial burden and functional disabilities. (Sampogna F et al, 2004; Mattoo SK et al, 2002; Mattoo SK et al, 2001) The Skindex-29 provides another validated quality-of-life metric that may address more of the emotional and psychosocial impact of the skin disease and has been applied in few vitiligo studies. (Ahmed A et al, 2013; Linthorst Homan MW et al, 2009)

While the exact etiology of vitiligo is unknown, the autoimmune hypothesis is the most supported. Both humoral and cellular immunity may contribute to the pathogenesis of the disease. Non-specific antibodies to the cell surface and intracellular pigment and non-pigment cell antigens have been found in the sera of the vitiligo patients. There had been evidence that melanocytes may be preferentially more susceptible to the immune-mediated injury than the other cell populations in the epidermis, keratinocytes and fibroblasts, ultimately leading to the vitiligo phenotype (Bystryn JC, 1989; Norris DA et al, 1988). Moreover, the increased levels of melanocyte-specific auto-reactive CD8+T cells that seem to correlate with disease severity have been shown in the peripheral blood of the vitiligo patients (Ogg GS et al, 1998; Palermo B et al, 2001; Lang KS et al, 2001). Recently, mouse models for vitiligo demonstrate that these auto-reactive T cells produce interferon gamma (IFN-gamma), which may be a crucial component to the migration and accumulation of the melanocytes-specific CD8+ T cells (Harris JE et al., 2012).

Histological and molecular analysis of vitiligo show impaired and absence of melanocytes, supported by molecular changes, such as the absence of KIT receptor, a protein expressed early in melanocyte differentiation, in vitiligo patients (Gokhale BB and Mehta LN, 1983). Perivascular inflammatory cell infiltrates have also been observed. Additional molecular difference between normal and vitiligo skin include decrease of stem cell factor (SCF), and increase levels of tumor necrosis factor-alpha (TNF-alpha) and interleukin-1 (IL-1) (Lee AY, 2012).

Genetic factors also have found to impact vitiligo. Epidemiologic studies in Caucasian families support that vitiligo is inherited in a non-Mendelian, multifactorial, polygenic pattern with incomplete penetrance (Alkhateeb A et al, 2003). Most cases of vitiligo are sporadic although familial clustering is not uncommonly seen.

Currently, reversing vitiligo depigmentation treatments, such as phototherapy psoralen plus ultraviolet (PUVA) and Narrow band UVB (NB-UVB) irradiation, is the most common medical therapy available for vitiligo. UVB phototherapy refers to the use of artificial UVB radiation in the treatment of medical conditions without the addition of exogenous photosensitizers. The radiation absorbed by endogenous chromophores, and the photo-chemical reactions involving these biomolecules mediate a variety of biological pathways, ultimately leading to the therapeutic effects. The mechanism of action of NB-UVB is not fully clear although in vitro studies provide support

that phototherapy stimulates melanocyte migration and proliferation and exhibit immunomodulating effects (Wu CS et al., 2007, Nishimura EK et al., 2002 and Chou WC et al., 2013). NB-UVB has also shown to promote repigmentation by inducing tyrosinase, an enzyme involved in melanin production, and increasing the presentation of HMB-45 marker on the surface of melanosomes (De Francesco V et al, 2008). Goldstein B et al., 2015 observes that vitiligo skin that received NB-UVB treatment of 3-6 months bring depigmented skin to normal status with no difference in melanocyte marker expression between treated and normal skin.

In addition, NB-UVB phototherapy is FDA-approved for both in-office and at-home treatment of vitiligo. The efficacy of NB-UVB phototherapy has been demonstrated in clinical studies, with heterogeneity among the trials with respect to disease severity, percent of body surface are affected, skin type, treatment, compliance, and outcome measures. In the 1997, Westerhof et al., first demonstrated that NB-UVB is effective in treating vitiligo. Most of the clinical studies on NB-UVB in vitiligo incorporated a comparator treatment group; rarely were there studies that compared NB-UVB with placebo in the treatment of vitiligo. Nevertheless, NB-UVB was found to be effective as monotherapy for vitiligo lesions and essentially a non-drug treatment that can be administered to patients quickly and safely (Yashar et al, 2003; Natta et al, 2003; Hamzavi et al, 2004; Kanwar et al, 2005; Parsad D et al, 2006; Bhatnagar et al, 2007; El-Zawahry BM et al, 2012).

4. Study Procedures

- a. Study design, including the sequence and timing of study procedures (distinguish research procedures from those that are part of routine care).
- b. Study duration and number of study visits required of research participants.
- c. Blinding, including justification for blinding or not blinding the trial, if applicable.
- d. Justification of why participants will not receive routine care or will have current therapy stopped.
- e. Justification for inclusion of a placebo or non-treatment group.
- f. Definition of treatment failure or participant removal criteria.
- g. Description of what happens to participants receiving therapy when study ends or if a participant's participation in the study ends prematurely.

This is an investigator-initiated, single-blinded, localized ascending dose study of NB-UVB treatment for vitiligo in adults of 3 treatments for one week. It is designed to measure the molecular changes and repigmentation in affected and normal skin of participants with vitiligo and normal skin in healthy participants. The study will collect questionnaire information, patient and clinical evaluations, and skin biopsies from each participant.

For all enrolled subjects, the starting dose will be 250 mJ/cm², which is the standard of care for patients with vitiligo. The dose will be increased by 10% with each treatment, as long as there are no side effects with treatment such as burning or redness/ erythema. Skin biopsies will be collected from normal skin and from affected skin from vitiligo patients, and from normal skin of healthy patients at the baseline visit and up to 1 week after the conclusion of treatment; up to a total of 6 biopsies will be collected from each patient. Collected tissue samples will undergo subsequent pathological examination or laboratory analysis. Recording of the initial treatment dose and the 10% increase in dosing per visit is tracked. All data collection is secured and stored in locked office of our Cutaneous Translational Research Program (CTReP).

Recruitment: Individuals will be recruited from the patient population seen at the general dermatology clinics of Johns Hopkins Department of Dermatology or from the patient population participating in Johns Hopkins Cutaneous Translational Research Program (CTReP) research studies. Potential participants will also be recruited if they are referred by other providers. Patients referred from other providers will have been asked their interest in learning more about the study and will have given their permission to be contacted by a study team member for more information. Participants will also be recruited from other patient populations at the Johns Hopkins Hospital and/or surrounding community through the use of advertisements. Interested individuals will be interviewed either in-person or over the telephone to see whether they meet basic eligibility criteria to participate in the study (see inclusion/exclusion criteria). Once eligibility has been demonstrated, the potential subjects will be directed to make their study appointment with an investigator.

Up to 20 healthy and vitiligo-diagnosed adult participants will be recruited. Interested, eligible participants will be invited to the initial visit, which will take place at the Cutaneous Translational Research Unit located at the Johns Hopkins Outpatient Center. At this appointment, to be conducted in a private exam room, the potential participant will be consented to participate in the study, for the collection of photographs, for administration of questionnaire, for an assessment of their skin, for phototherapy, and for skin biopsies. Prior to NB-UVB treatment, baseline biopsies will be obtained from normal and affected skin sites of vitiligo patients and normal skin of healthy patients. NB-UVB treatment will be administered on selected skin areas by research personnel. Patient will receive two additional NB-UVB treatments within the same week to total 3 treatments in a week, a typical schedule used in the treatment of vitiligo. Up to a week after the last treatment, biopsies will be obtained from treated skin regions. About 10 days after the biopsy, patient will return for suture removal.

Questionnaire: A questionnaire on basic demographic information and past dermatologic history will be administered to subjects by CTReP investigators. Subjects will also be able to complete the questionnaire by themselves. Questionnaire data will be coded and stored on a secure hard drive managed by the CTReP staff.

Device: The 3 Series PC & SP phototherapy cabinet is a microprocessor controlled full body fluorescent ultraviolet light source, with spectral output at peak wavelength of 311 nm (Narrow Band UVB). It is intended for use by or under the direction of a physician, for the treatment of psoriasis, vitiligo, and atopic dermatitis (eczema). The desired dose is selected using the operator interface located on the front panel of the device. The 3 Series delivers full body phototherapy, whereby fluorescent tubes, which surround the patient, deliver the specified dose of UVB.

Photographs: Digital photographs will be obtained by study staff of each participant, at skin regions of vitiligo and normal skin, such as the extremities and trunk that are receiving treatment and areas of biopsy. Photograph files will be stored on a secure hard drive in the CTReP.

Skin biopsies: Up to six 4mm-punch biopsies will be performed at normal skin region and from treated vitiligo lesions for vitiligo patients or at normal skin for healthy patients: up to 3 biopsies will be obtained from each subject prior to NB-UVB treatment and up to 3 biopsies will be obtained up to one week after the last treatment. Biopsies will undergo subsequent pathological examination or laboratory analysis to assess for molecular change and repigmentation. The punch biopsy is a routine dermatological procedure consisting of local anesthesia with 1% lidocaine, followed by the punch which cuts a cylindrical core of epidermis, dermis, and

subcutaneous tissue. After removal of the tissue sample, a 4-0 suture is placed to close the circular opening on the arm (5-0 suture is used on the face). Ten days after the procedure, the sutures are removed. A 3-4 mm scar is formed, but typically blends well with the surrounding skin and becomes difficult to appreciate.

Laboratory studies: Microscopic and/or immunohistochemical studies may be conducted on pathology slides obtained from biopsy specimens, and photographs of pathology slides may be taken. Biopsy specimens may also be molecularly evaluated for protein and gene expression. Remaining tissue material may be anonymously stored for use in future studies. Using collected skin biopsy samples, various biochemical markers of phototherapy-induced or other cellular characteristics may be studied. Examples may include expression of melanocyte and keratinocyte markers, and migration of cells within the intra-epidermal and sub-epidermal regions.

Objective Assessment/ Evaluation: Objective assessment of protein and gene expression will be conducted as above. The investigators performing the molecular testing will be blinded to the disease status and treatment status of the tissue.

5. Inclusion/Exclusion Criteria

Inclusion Criteria

- Adults 18 years or older with bilateral symmetrical vitiligo lesions, in general good health as determined by the Principal Investigator by medical history and physical exam.
- Able to understand consent procedure
- Able to comply with protocol activities

Exclusion Criteria

- Patients less than 18 years old
- Patients not able to understand consent procedure
- Patients unable to comply with protocol activities
- Non-English speakers: the study assessments/questionnaires/evaluations are not scientifically validated in languages other than English. Given the lack of translators in over 50% of patient encounters in the dermatology clinic and the interpreters' limited time commitments when one does show up, it is impossible to safely enroll or follow patients who do not speak English. Phone translators are impossible given that we have written consent forms, which often exceed 10 pages in length.
- Patients with a photosensitive disorder or on a medication which has been demonstrated in these patients to cause photosensitivity
- Patients receiving concomitant phototherapy to test sites
- Patient receiving topical medication to test sites within 2 weeks of study initiation
- Patient receiving oral medications for vitiligo within 4 weeks prior to study initiation
- Receipt of an investigation agent within the past 4 weeks (or within 5 half lives) prior to study initiation
- Pregnant or nursing patients (self-reported)
- Patient with significant medical history or concurrent illness that the investigator feels is not safe for study participation, including melanoma
- Presence or suspicion of bleeding disorder or diathesis which would complicate biopsy.
- Patients with history of excessive scar or keloid formation in the past 10 years
- Patients with known allergy to anesthetic used

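### Phototherapy to test sites is excluded only while concomitant, with no look-back, so the baseline lesional biopsy may come from recently phototreated skin

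*Combined protocol and SAP*

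**What the plan says.** Section 5 (Exclusion Criteria) has four neighbouring items on other treatment:

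- Phototherapy: "Patients receiving concomitant phototherapy to test sites". No period is given.
- Topical treatment: "Patient receiving topical medication to test sites within 2 weeks of study initiation".
- Oral treatment: "Patient receiving oral medications for vitiligo within 4 weeks prior to study initiation".
- Investigational treatment: "Receipt of an investigation agent within the past 4 weeks (or within 5 half lives) prior to study initiation".

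The Abstract (Section 1) hypothesises, after one week of NB-UVB, "observable molecular changes in vitiligo-treated skin when compared to vitiligo untreated and normal skin". It also says that NB-UVB "is the most common medical therapy available for vitiligo".

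Section 4 (Recruitment) gives the tissue schedule. Before NB-UVB, "baseline biopsies will be obtained from normal and affected skin sites of vitiligo patients and normal skin of healthy patients". Afterwards, "Up to a week after the last treatment, biopsies will be obtained from treated skin regions". It also provides for an eligibility interview and a questionnaire that covers past dermatologic history. Section 7 names no primary contrast between these samples.

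**The concern.** Three kinds of earlier treatment have a look-back. The treatment under study does not. Read as written, the rule bars a patient who is receiving phototherapy at the test site, but not one whose course there has just ended.

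The tissue most exposed to this gap is the baseline lesional biopsy. If it already reflects recent NB-UVB, the difference between it and the post-treatment biopsy is no longer the effect of the first week of treatment. Comparing each patient with himself or herself removes stable differences between patients. It does not remove a recent exposure at the same site. Blinding the laboratory to disease and treatment status does not help either, because the tissue itself would differ. Once study treatment has begun, the baseline sample cannot be retaken.

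**Working it through.** The documents state no figure on this point, so the check is mainly a comparison of sections.

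1. **Is there a phototherapy-free interval elsewhere?** The recruitment, device, biopsy and statistics text contains none. The investigational-agent criterion does not supply one for routine care, because Section 3 describes NB-UVB as FDA-approved for vitiligo, both in the office and at home.

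2. **Is the baseline biopsy the untreated reference?** The hypothesis needs untreated vitiligo skin. The post-treatment biopsies are described only from treated regions. The pre-treatment lesional biopsy is therefore the only lesional sample described as free of study treatment. This role is inferred; Section 7 does not define it. If an untreated lesion on the opposite side were used instead (inclusion requires bilateral symmetrical lesions), no look-back would protect that site either.

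3. **Could recent exposure show in that sample?** Section 3 reports that NB-UVB induces tyrosinase and raises HMB-45, and Section 4 lists melanocyte markers among its example readouts. The design itself expects three sessions to leave a signal that can still be measured up to a week after the last one. On that premise, phototherapy that ended shortly before baseline cannot be assumed to leave no trace.

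4. **Is recent exposure plausible?** The protocol calls NB-UVB the most common medical therapy for vitiligo. It recruits from dermatology clinics, the unit's own research studies and referring providers. No section says what share of patients was recently treated.

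5. **Does an existing safeguard act on it?** The interview applies the listed criteria, none of which looks back for phototherapy. The medical history and the questionnaire may reveal earlier courses, but no criterion or analysis uses that information.

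**Illustration only.** Let n be the number of vitiligo participants, p the share recently phototreated at the test site, and r the fraction by which their first-week response is reduced. All three are assumptions. The protocol gives at most 20 participants in total with no vitiligo/healthy split, no exposure rate and no data on persistence. With n = 10:

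- expected number exposed = n × p
- chance of at least one = 1 − (1 − p)^10
- attenuation of the mean change = p × r

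| p | Expected exposed | At least one | Attenuation, r = 25% | Attenuation, r = 50% |
|---|---|---|---|---|
| 2% | 0.2 | 18% | 0.5% | 1% |
| 5% | 0.5 | 40% | 1.25% | 2.5% |
| 10% | 1.0 | 65% | 2.5% | 5% |
| 25% | 2.5 | 94% | 6.25% | 12.5% |

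One exposed participant shifts the mean change by r/n, which is 0.25/10 = 2.5% to 0.50/10 = 5%. If earlier exposure raises the response instead, these are inflations of the same size.

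**The case against.** The case on the other side has several parts.

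- **The gap may be narrow.** The word concomitant is undefined, and the protocol calls three sessions a week a typical schedule. An investigator could reasonably treat a patient between sessions as receiving concomitant phototherapy, so the most exposed patients are already out. This stands: the gap clearly concerns only patients who have stopped. It does not close the gap, because no definition turns the word into a look-back.

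- **The evidence for carry-over is indirect.** The strongest result in Section 3 concerns 3-6 months of treatment that brought depigmented skin back to normal. A site restored that far would not be sampled as affected skin. Nothing is said about how long markers stay altered in skin that remains depigmented. This also stands, and it is why the point says only that the baseline may be altered.

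- **The numbers carry no weight.** No exposure rate or persistence is documented, and low values of p give small effects. This is correct. The table shows how the formulas behave and does not estimate the bias.

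- **History is already taken.** That helps to describe exposure, but nothing in the plan acts on it.

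- **A look-back could lead patients to interrupt routine phototherapy in order to qualify.** This is a fair cost. The heading list of Section 4 asks for stopped therapy to be justified.

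A reader might infer that the lesional before/after contrast is the study's designated primary comparison. The documents do not go that far: the hypothesis also names normal skin, healthy participants are sampled, and Section 7 designates no contrast.

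**Conclusion.** The concern holds as a correctable gap in eligibility. As written, the rule admits a patient whose test site was phototreated until shortly before baseline, and the implied untreated reference may then not be free of NB-UVB effects. The one-week change could be biased. The number affected and the size and direction of the bias cannot be determined from the documents, and the bias may be small if recent exposure is rare.

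This rests on two readings: that concomitant means ongoing, and that untreated vitiligo skin means the pre-treatment lesional biopsy.

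Two stronger conclusions are tempting and not supported. One is that the baseline samples are contaminated; the documents show only that the rule allows it. The other is that the treatment effect will be understated. That would follow if markers were already shifted towards their treated level, but earlier exposure could also heighten the response, and no section settles which.

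**What to change.** Extend the existing exclusion to phototherapy received at any test site, lesional or normal, within a stated period before the baseline biopsy, in the same form as the neighbouring criteria. The investigators should set the length and justify it. Normal sites belong in the rule because they are also biopsied, and a course given in a full-body cabinet such as the study device would reach them too.

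Ask about such exposure at the eligibility interview. Record the date and body site of the last phototherapy in the dermatologic-history questionnaire, so that any earlier exposure that remains can be described with the results. A comparison with and without exposed participants is optional: it is largely redundant once the exclusion applies, and with so few participants it would be imprecise.

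On paper this costs one eligibility line and one questionnaire item. The real cost is recruitment. Some vitiligo patients become ineligible or enter later: on the assumed values with 10 vitiligo participants, 10 × 2% = 0.2 to 10 × 25% = 2.5 people. If the look-back could lead patients to pause routine phototherapy, the protocol should address that too.
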